2.2 Secondary estimands

Not applicable.

3 Study design

The study is an international, multi-center, non-comparative, phase IIIb, treatment optimization study of asciminib (randomized 1:1 to either 40 mg b.i.d. or 80 mg q.d.) in adult patients previously treated with 2 or more TKIs. Randomization is only used to have a balance in the allocation of treatment into either asciminib 40 mg b.i.d. or 80 mg q.d.

In patients not achieving MMR at 48 weeks or losing the response after the week 48 assessment up to week 108, asciminib dose may be escalated to 200 mg q.d. if in the investigator's opinion the patient may benefit from the escalation. In addition, there must not be any grade 3 or 4 toxicity while on therapy, or persistent grade 2 toxicity, possibly related to asciminib and unresponsive to optimal management.

[figure not shown]
BCR-ABL1 and **CCI** results are required before increasing asciminib dose, therefore the dose escalation can occur at next scheduled visit upon results review of the prior visit. In patients losing response after the week 48 assessment, the last possible time point to initiate the 200 mg dose will be the week 120 visit to ensure that efficacy and safety of the dose escalation can be sufficiently established during the remaining trial follow up period.

If a dose decrease is required, patients will return to the initial dosing regimen (q.d. or b.i.d.) they were using before the dose increase which was considered tolerable. For this reason, if a patient e.g. escalates from 40 mg b.i.d. to 200 mg q.d., in case of a required dose decrease a use to 80 mg q.d. is not allowed and the patient will continue on 40 mg b.i.d. asciminib.

All patients will be treated for a maximum duration of 144 weeks.

The primary endpoint of the study is MMR rate at 48 weeks. As the ELN 2020 recommendations do not give specific treatment guidance for milestones in 3rd line, the ELN 2020 milestone at twelve months for optimal response in 2nd and 1st line was chosen to define the primary endpoint.

Figure 3-1 Study design

*Treatment assignment to b.i.d. or q.d. (1:1) will be done through Interactive Response Technology (IRT).

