6.6.3 Dose modifications

For participants who do not tolerate the protocol-specified dosing schedule, dose interruptions, and/or reductions are either recommended or mandated in order to allow participants to continue the study treatment.

Table 6-3 Dose reduction schedule

*Dose reduction			
		Starting dose level 0	Dose level – 1
Asciminib	CML-CP	40 mg b.i.d. (total daily dose 80 mg)	20 mg b.i.d. (total daily dose 40 mg)
	CML-CP	80 mg q.d. (total daily dose 80 mg)	40 mg q.d. (total daily dose 40 mg)
	CML-CP	200 mg q.d. (total daily dose 200 mg)	80 mg q.d. or 40 mg b.i.d. (total daily dose 80 mg)**
*Dose reduction should be based on the worst toxicity demonstrated at the last dose.			
**Patients on 200 mg q.d. needing a dose de-escalation will revert to 80 mg total daily dose of asciminib, according to pre-escalation dosing schedule (q.d. or b.i.d. regimen assigned at enrollment).			
Asciminib dose reduction below total daily dose of 40 mg (20 mg b.i.d. or 40 mg q.d.) is not allowed. 20 mg tablets will be dispensed to patients having 20 mg b.i.d. regimen in the instance of dose reduction.			

These dose modifications, in addition to permanent treatment discontinuations, are summarized in (Table 6-4). Deviations to mandatory dose interruptions and/or reductions are not allowed.

These dose changes must be recorded on the appropriate CRF.

A patient must discontinue treatment with asciminib if, after treatment is resumed at a lower dose level, the toxicity recurs with the same or worse severity, except for recurrence of cytopenias (Table 6-4). If a patient requires a dose interruption of > 28 days for each non-hematologic toxicity, then the patient must be discontinued from the study treatment. If a hematologic toxicity (cytopenia Grade 3 or 4) last for more than 42 days without recovery to at least a Grade 2, despite asciminib interruption and adequate management (including hematopoietic growth factors), then the patient must be discontinued from study treatment.

Table 6-4 Criteria for dose reduction / interruption / discontinuation and re-initiation of treatment for adverse drug reactions

Dose modifications for asciminib	
Please note that if a patient requires a dose interruption of > 28 days for any toxicity, and > 42 days for hematologic toxicity, then the patient should be discontinued from study treatment	
Worst toxicity CTCAE Version 5.0	Asciminib

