1.1 Study design

The study is an international, multi-center, non-comparative, phase IIIb, treatment optimization study of asciminib (randomized 1:1 to either 40 mg b.i.d. or 80 mg q.d.) in adult subjects previously treated with 2 or more TKIs. 156 subjects will be randomized to either asciminib 40 mg b.i.d. or 80 mg q.d. An additional 30 subjects (randomized to either asciminib 40 mg b.i.d. or 80 mg q.d.) intolerant only to last TKI and in MMR at baseline will also be included.

Randomization is only used to have a balance in the allocation of treatment into either asciminib 40 mg b.i.d. or 80 mg q.d. The trial will not be powered to compare both treatments.

In subjects not achieving MMR at 48 weeks or losing the response after the week 48 assessment up to week 108, asciminib dose may be escalated to 200 mg q.d. if in the investigator's opinion

the subject may benefit from the escalation. In addition, there must not be any grade 3 or 4 toxicity while on therapy, or persistent grade 2 toxicity, possibly related to asciminib and unresponsive to optimal management.

[figure not shown]
BCR::ABL1 and **CCI** results are required before increasing asciminib dose, therefore the dose escalation can occur at next scheduled visit upon results review of the prior visit. In subjects losing response after the week 48 assessment, the last possible time point to initiate the 200 mg dose will be the week 120 visit to ensure that efficacy and safety of the dose escalation can be sufficiently established during the remaining trial follow up period.

If a dose decrease is required, subjects will return to the initial dosing regimen (q.d. or b.i.d.) they were using before the dose increase which was considered tolerable. For this reason, if a subject escalates from 40 mg b.i.d. to 200 mg q.d., in case of a required dose decrease, use of 80 mg q.d. is not allowed and the subject will continue 40 mg b.i.d. asciminib.

All subjects will be treated for a maximum duration of 144 weeks.

The primary endpoint of the study is MMR at 48 weeks.

Figure 1-1 Study design

*Treatment assignment to 40 mg b.i.d. or 80 mg q.d. (1:1) will be done through Interactive Response Technology (IRT).

Three analyses are planned for this study, including the 48-week primary analysis, the 96-week analysis, and the End-of-Study-Treatment (EOsT) analysis. The timing when those analyses are conducted is summarized in Section 2.1.

No formal interim efficacy analysis is planned in this study.

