2.1.1 General definitions

Investigational drug and study treatment

Investigational drug, will refer to asciminib. No additional treatment beyond investigational drug is included in this trial.

Treatment groups

- Asciminib 40 mg b.i.d. (Subjects randomized to asciminib 40 mg b.i.d. at the beginning of the study)
- Asciminib 80 mg q.d. (Subjects randomized to asciminib 80 mg q.d. at the beginning of the study)

The standard dose for all subjects in this study is asciminib 40 mg b.i.d. or 80 mg q.d. For subjects not achieving MMR at 48 weeks or losing the response after the week 48 assessment up to week 108, a dose escalation to 200 mg q.d. may be considered per investigator decision.

Date of end of study treatment (EOsT)

The EOsT date is the date that the study treatment is ended for the entire study. On this date, subjects are treated for at maximum 144 weeks, unless subjects have discontinued study treatment earlier.

Date of first administration of study treatment

The date of first administration of study treatment is derived as the first date when a non-zero dose of study treatment was administered as per the Study Treatment electronic case report form (eCRF). The date of first administration of study treatment will also be referred as start of study treatment.

The date of first administration of study treatment is the same as the date of first administration of investigational drug.

Start Date of dose escalation

The start date of dose escalation is derived as the first date when a subject had dose escalated to 200 mg q.d. of study treatment as per the Subject Status Dose Escalation case report form (eCRF).

Date of last administration of study treatment

The date of last administration of study treatment is defined as the last date when a non-zero dose of study treatment was administered as per Study Treatment eCRF.

The date of last administration of study treatment is the same as the date of last administration of investigational drug.

Study day

The study day, describes the day of the event or assessment date, relative to the reference start date.

The study day is defined as:

- The date of the event (visit date, onset date of an event, assessment date, etc.) – reference start date + 1 if event is on or after the reference start date;
- The date of the event (visit date, onset date of an event, assessment date, etc.) – reference start date if event precedes the reference start date.

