The reference start date for safety assessments (e.g. adverse event onset, laboratory abnormality occurrence, vital sign measurement, dose interruption, etc.) is the start of study treatment.

The reference start date for all other, non-safety assessments (e.g. molecular response, disease progression, ECOG performance status, patient reported outcomes (PRO), etc.) is the date of randomization.

The reference start date for dose escalation (200 mg q.d.) is the date when a subject starts first escalated dose.

The study day will be displayed in the data listings. If an event starts before the reference start date, the study day displayed on the listing will be negative.

Time unit

A year length is defined as 365.25 days. A month length is 30.4375 (=365.25/12) days. If duration is reported in months, duration in days will be divided by 30.4375. If duration is reported in years, duration in days will be divided by 365.25.

A week length is defined as 7 days. If duration is reported in weeks, duration in days will be divided by 7.

Baseline for the treatment period

For efficacy evaluations, the last non-missing assessment, including unscheduled assessments on or before the date of randomization is taken as “baseline” value or “baseline” assessment. In the context of baseline definition, the efficacy evaluations also include PRO and performance status.

For safety evaluations, the last available assessment, including unscheduled assessments before the date of start of study treatment is taken as “baseline” assessment.

For pre-dose electrocardiogram (ECG), the last available assessment before the treatment start date is used for baseline.

For ECGs requiring triplicate measures per time point, the average of these measurements will be reported by sites in eCRF baseline.

For mutations, the screening/baseline assessment is taken as “baseline” assessment.

In rare cases where multiple laboratory measurements meet the baseline definition, with no further flag or label that can identify the chronological order, then the following rule should be applied: If values are from central and local laboratories, the value from central assessment should be considered as baseline.

If subjects have no value as defined above, the baseline result will be missing.

On-treatment assessment/event and observation periods

For adverse event reporting the overall observation period will be divided into three mutually exclusive segments:

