1. ***pre-treatment period:*** from day of subject’s informed consent to the day before first administration of study treatment
2. ***on-treatment period:*** from date of first administration of study treatment to 30 days after date of last administration of study treatment (including start and stop date).
3. ***post-treatment period:*** starting at day 31 after last administration of study treatment.

If dates are incomplete in a way that clear assignment to pre-, on-, post-treatment period cannot be made, then the respective data will be assigned to the on-treatment period.

Safety summaries (tables, figures) on the corresponding Safety set include only data from the on-treatment period with the exception of baseline data which will also be summarized where appropriate (e.g. change from baseline summaries). In particular, summary tables for adverse events (AEs) will summarize only on-treatment events, with a start date during the on-treatment period. In addition, a separate summary for death will be provided.

However, all safety data (including those from the pre-treatment and post-treatment) will be listed and flagged as appropriate.

Efficacy summaries on the FAS and FAS 2 (apart from OS and PFS) include data from baseline up to either the last assessment on or before the End of Treatment (EoT) visit or before or on treatment failure, whichever is the earliest.

The efficacy assessments collected post-treatment failure or post-EoT visit are not included in any efficacy analyses (except for OS and PFS analyses). However, they will be listed and flagged as appropriate.

Windows for multiple assessments

Data such as molecular response, cytogenetic response collected over time (including unscheduled visits) will be summarized by scheduled time point. As subjects do not always adhere to the visit schedule, visits will be remapped according to visit windows defined in Tables 2-1 to Table 2-3 of this document to enable by-visit analysis. Only those protocol-defined visits will have the visit window defined. Each assessment (including the end of treatment assessment), either scheduled or unscheduled, will have a mapped visit assigned, as long as study day is available, according to the defined visit window up to the date with data included.

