2.7 Safety analyses

For all safety analyses, the Safety set (SAF, SAF 2) will be used, except where stated otherwise.

Safety summaries (tables, figures) include only data from the on-treatment period with the exception of baseline data which will also be summarized where appropriate (e.g. change from baseline summaries). In addition, a separate summary for death including on treatment and post treatment deaths will be provided. In particular, summary tables for adverse events (AEs) will summarize only on-treatment events, with a start date during the on-treatment period (treatment-emergent AEs).

The overall observation period will be divided into three mutually exclusive segments:

1. Pre-treatment period: from day of participant's informed consent to the day before first dose of study medication
2. On-treatment period: from day of first dose of study medication to 30 days after last dose of study medication
3. Post-treatment period: starting at day 31 after last dose of study medication.

The following will also be summarized for a) **all** subjects using combined sets (SAF and SAF 2), for b) SAF 2 only, for c) subjects by dose escalation status (with or without dose escalation) and for d) only for subjects with dose escalation (prior to and after dose escalation):

- All deaths
- Serious adverse events and adverse events of special interest
- Adverse events leading to treatment discontinuation
- Grade 3 and 4 adverse events

Analysis of ECG data, for dose escalation is mentioned in [section 2.7.4.1](#).

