A summary table with descriptive statistics for LVEF at different timepoints (screening/baseline, Week 48 (+/- 4 weeks) and end of treatment visit) and for change from baseline will be presented. A shift table for LVEF categories ($\leq 40\%$, 41-49%, $\geq 50\%$) at baseline versus worst value on treatment will also be presented.

ECG assessment needs are similar for all subjects up to week 48.

For subjects with dose escalation, ECG assessments will be performed at:

- on the day of dose escalation (pre-dose and between 2h to 3h post-dose ECGs are required),
- two weeks post-dose escalation,
- at next 2 quarterly visits (at 3 and 6 months post-dose escalation),
- every 6 months thereafter.

The above described analyses for ECG data will also be performed separately for a) subjects by dose escalation status (with or without dose escalation) and for b) only for subjects with dose escalation (prior to and after dose escalation).

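### The SAP's post-escalation safety and ECG summaries have a start but no end, so data obtained after a return from 200 mg to 80 mg are pooled with data on 200 mg

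*Protocol*

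**What the plan says.** **A return from 200 mg is planned for.** Protocol 6.6.3 (Table 6-3) states: "Patients on 200 mg q.d. needing a dose de-escalation will revert to 80 mg total daily dose of asciminib, according to pre-escalation dosing schedule". Protocol Section 3, Section 6.1.1 and Table 6-2 agree, and SAP 1.1 repeats it: "If a dose decrease is required, subjects will return to the initial dosing regimen (q.d. or b.i.d.) they were using before the dose increase". The patient stays on study treatment.

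**Escalation has a start date only.** SAP 2.1.1: "The start date of dose escalation is derived as the first date when a subject had dose escalated to 200 mg q.d". For study days it adds: "The reference start date for dose escalation (200 mg q.d.) is the date when a subject starts first escalated dose". Neither document defines an end-of-escalation or de-escalation date for analysis. The only closing rule that applies is the general on-treatment period, which runs "from date of first administration of study treatment to 30 days after date of last administration of study treatment".

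**The split has two periods.** SAP 2.7 lists deaths, SAEs and AESIs, AEs leading to discontinuation, and grade 3 and 4 AEs, to be summarised among other ways "for d) only for subjects with dose escalation (prior to and after dose escalation"). SAP 2.7.4.1 repeats the ECG analyses "for b) only for subjects with dose escalation (prior to and after dose escalation").

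**What is available elsewhere.** SAP 2.4.1 lists every dose with the reason for change and summarises reductions. SAP 2.7.1 summarises AEs leading to dose interruption or adjustment. No safety or ECG summary is by dose at onset or dose at assessment.

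**The concern.** Dose escalation is one of the study's stated purposes (Protocol 1.2). Protocol Section 3 sets the last escalation visit at week 120 "to ensure that efficacy and safety of the dose escalation can be sufficiently established during the remaining trial follow up period". Earlier experience with 200 mg q.d. described in Protocol 4.2 is 12 phase I patients. The before/after tables are the planned within-patient evidence on safety after escalation, and readers will take them as the evidence on 200 mg.

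For a subject who goes back to 80 mg, the second period contains two doses. The mixing is greatest in those who left 200 mg earliest. Two examples show how it enters:

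- Protocol 6.6.3 requires discontinuation if a toxicity recurs at the same or worse severity after resuming at a lower dose (cytopenias excepted). Such an AE, starting on 80 mg, would be tabulated as leading to discontinuation after escalation.
- A subject reduced because of QTcF keeps contributing ECGs at later post-escalation visits, now on 80 mg.

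The first adds to the counts. The second can dilute a 200 mg signal at a given time point. The direction of the net bias is therefore not fixed.

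**Working it through.** The plan gives no figure on this point, so there is none to reproduce. The check is a reading of the period rules, followed by an illustration.

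**Step 1: which period receives 80 mg data after a return?**

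| Rule | Start | End |
|---|---|---|
| Escalation (SAP 2.1.1) | first 200 mg date | none given |
| On-treatment period (SAP 2.1.1, 2.7) | first dose | 30 days after last dose of study treatment |
| Planned dose at 200 mg/day (SAP 2.4.1) | escalation start | last study treatment date |

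An AE or ECG on 80 mg after a return is on treatment, and it is later than the escalation start. With two periods only, it falls in the second. The SAP does not say this in words; it follows from a start date without an end. The planned-dose rule reads the same way, since it counts all exposure since escalation at 200 mg/day.

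**Step 2: how much of the second period can be 80 mg time, per subject?**

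Inputs:
- Escalation week e runs from 60 to 120 (Protocol Table 6-2, footnote).
- Maximum treatment is 144 weeks (Protocol Section 3, SAP 1.1).
- Weeks on 200 mg before return, t, is assumed to be 2, 12 or 24.
- The subject completes week 144, and any dose hold is ignored (both assumed).

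Formulas: post-escalation dosing days = 7 × (144 − e). Days on 80 mg = 7 × (144 − e − t). Share on 80 mg = 1 − t/(144 − e).

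| e | Dosing days | t = 2 | t = 12 | t = 24 |
|---|---|---|---|---|
| 60 | 588 | 574 (98%) | 504 (86%) | 420 (71%) |
| 84 | 420 | 406 (97%) | 336 (80%) | 252 (60%) |
| 120 | 168 | 154 (92%) | 84 (50%) | 0 (0%) |

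For e = 60 the whole window is 588 + 30 = 618 days.

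**Step 3: across all escalators.** Let f be the fraction who return (assumed; the documents give no rate). With e = 60 and t = 12 for every returner, and everyone completing, the share of post-escalation dosing time on 80 mg = f × (84 − 12)/84:

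- f = 10%: 0.10 × 72/84 = 9%
- f = 20%: 17%
- f = 30%: 26%
- f = 50%: 43%

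**Step 4: what is not affected.** Escalation starts at week 60 at the earliest, so the week 48 MMR endpoint and its sample size do not change.

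**The case against.** The best defence is that the label is true in time. No SAP table is headed as safety on 200 mg, and the protocol speaks of the safety of the escalation, which can be read as a strategy with return to 80 mg built in. None of the unredacted objectives is specific to 200 mg. The summaries are descriptive, and dose at onset can be recovered from listings. All of this stands. It justifies keeping the combined column, but it does not give the reader a table for 200 mg itself.

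It is also fair that the week 60 completer is the long end of the range. Escalation can come as late as week 120, and Protocol 9.1.1 and 6.6.3 stop some of these patients early. The size is therefore illustrative.

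Three stronger inferences are tempting and are not supported:

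- **That the pooled column inflates 200 mg harm about fivefold.** For an AE at an assumed 0.5 per year at either dose, the chance is 1 − exp(−0.5 × 12/52.18) = 11% over 12 weeks and 1 − exp(−0.5 × 84/52.18) = 55% over 84 weeks. That gap is length of follow-up: a subject who stayed on 200 mg for all 84 weeks would also have 55%.
- **That the phase I cohort bounds the number returning.** Protocol 4.2 reports grade 3 or higher AEs in 8 of 12 patients regardless of relationship to treatment. Table 6-4 concerns adverse drug reactions, sends many severe events to permanent discontinuation, and reduces the dose for some lower-grade ones. So 8/12 is neither a bound nor a rate.
- **That ECGs on 200 mg and 80 mg are averaged within a patient.** SAP 2.7.4.1 averages the triplicate at one time point (and unscheduled ECGs close together on one day) and summarises change by time point. What is pooled is subjects on different doses at the same time point, and notable values in the subject counts.

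**Conclusion.** The gap is real and worth closing. For subjects who return from 200 mg to 80 mg, the post-escalation AE and ECG summaries combine both doses until 30 days after the last dose, and no planned summary separates them. The tables therefore cannot show safety at 200 mg itself.

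The size is unknown because the documents give no return rate, and few subjects may be affected. With return after 12 weeks from a week 60 escalation and completion of week 144 (all assumed), 86% of that subject's post-escalation dosing days are on 80 mg. At assumed return rates of 10% and 30%, the share across escalators is 9% and 26%. The documents do not support saying that the tables overstate or understate the risk at 200 mg; either can happen. The primary analysis is unaffected.

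**What to change.** This changes analysis periods only and touches no dosing rule.

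1. In SAP 2.1.1, define the date of the first dose at 80 mg or lower after 200 mg, taken from the Study Treatment eCRF.
2. In SAP 2.7 d) and 2.7.4.1 b), divide the post-escalation time into two contiguous periods:
   - **200 mg period:** from the first 200 mg dose to the day before the first reduced dose, including any dose hold. If the subject stops treatment directly from 200 mg, it runs to 30 days after the last dose.
   - **After return to 80 mg or lower:** from the first reduced dose to the end of the on-treatment period.
3. Assign AEs by start date and ECGs by assessment date.
4. Pre-state a carry-over rule for AEs that start soon after the return.
5. Keep the whole post-escalation column as a second summary, labelled as covering both doses.

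The periods need to be contiguous. If the first ended at the last 200 mg dose, AEs during a hold would belong to neither period, and neither would AEs in the 30 days after stopping directly from 200 mg.

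The cost is SAP wording and one extra column from dosing dates already collected. The downside is smaller counts per column.

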Investigations (hematologic): If a hematologic toxicity (cytopenia grade 3 or 4) lasts for more than 42 days without recovery to at least grade 2, despite asciminib interruption and adequate management (including hematopoietic growth factors), then the patient should be discontinued from study treatment.	
Neutropenia (ANC)	
Grade 1 (ANC < LLN – 1.5 x 10 ⁹ /L)	Recommendation: Maintain dose level
Grade 2 (ANC < 1.5 – 1.0 x 10 ⁹ /L)	Recommendation: Maintain dose level
Grade 3 (ANC < 1.0 – 0.5 x 10 ⁹ /L)	Mandatory: Hold dose until resolved to grade ≤ 2 (recheck CBC 2x/week), then: if resolved in ≤ 14 days, then maintain dose level If resolved in > 14 days, then reduce dose ↓ 1 dose level
Grade 4 (ANC < 0.5 x 10 ⁹ /L)	Mandatory: Hold dose until resolved to grade ≤ 2, (recheck CBC 2x/week), then: if resolved in ≤ 14 days, then maintain dose level if resolved in > 14 days, then reduce dose ↓ 1 dose level

Dose modifications for asciminib	
Please note that if a patient requires a dose interruption of > 28 days for any toxicity, and > 42 days for hematologic toxicity, then the patient should be discontinued from study treatment	
Worst toxicity CTCAE Version 5.0	Asciminib
Febrile neutropenia (ANC < 1.0 x 10 ⁹ /L, fever ≥ 38.5°C)	Mandatory: Hold dose until resolved, then reduce dose ↓ 1 dose level
Thrombocytopenia	
Grade 1 (PLT < LLN – 75 X 10 ⁹ /L)	Recommendation: Maintain dose level
Grade 2 (PLT < 75 - 50 x 10 ⁹ /L)	Recommendation: Maintain dose level
Grade 3 (PLT < 50 - 25 x 10 ⁹ /L)	Mandatory: Hold dose until resolved to grade ≤ 2 (recheck CBC 2x/week), then: if resolved in ≤ 14 days, then maintain dose level if resolved in > 14 days, then reduce dose ↓ 1 dose level
Grade 4 (PLT < 25 x 10 ⁹ /L)	Mandatory: Hold dose until resolved to grade ≤ 2 (recheck CBC 2x/week), then: if resolved in ≤ 14 days, then maintain dose level if resolved in > 14 days, then reduce dose ↓ 1 dose level
Recurrence of any cytopenia	Recommendation: Hold dose until resolved to grade ≤ 2, then maintain current dose level For recurrent Grade 3/4 cytopenia, please refer to above guidelines for neutropenia and thrombocytopenia; no further dose reduction is allowed for already reduced dose.
Non-hematologic adverse reactions except where further specified in individual sections	
Grade 1	Recommendation: Maintain dose level
Grade 2	Recommendation: Hold dose until resolved to grade ≤ 1, then maintain dose level
Grade 3	Mandatory: Hold dose until resolved to grade ≤ 1, then reduce dose ↓ 1 dose level

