2.5.3 Handling of intercurrent events

The approach of accounting for intercurrent events is as follows:

- **For the intercurrent events 4a:** The composite strategy will be applied for treatment discontinuation due to any reason. Treatment discontinuations due to any reason will be defined as non-responders.
- **For the intercurrent events 4b:** The treatment policy strategy will be applied. Meaning, the actual values of the variable (BCR::ABL1 % IS) will be used, regardless of whether the intercurrent event has occurred.
- **For the intercurrent events 4c:** The treatment policy strategy will be applied. Meaning, the actual values of the variable (BCR::ABL1 % IS) will be used, regardless of whether the intercurrent event has occurred.

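### For a patient already at 40 mg daily with a new toxicity, Table 6-4's mandatory one-level reduction cannot be reconciled at restart with Table 6-3's 40 mg floor, so sites may stop or continue the same patient

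*Protocol*

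**What the plan says.** Protocol Table 6-3 gives patients who start on 80 mg a single reduced level, 40 mg total daily dose, and closes the scale there: "Asciminib dose reduction below total daily dose of 40 mg (20 mg b.i.d. or 40 mg q.d.) is not allowed". The text of 6.6.3 adds that "Deviations to mandatory dose interruptions and/or reductions are not allowed".

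Table 6-4 then prescribes reductions by toxicity. The general grade 3 non-hematologic row reads "Mandatory: Hold dose until resolved to grade ≤ 1, then reduce dose ↓ 1 dose level". The febrile neutropenia row reads "Mandatory: Hold dose until resolved, then reduce dose ↓ 1 dose level". Many organ-specific rows end the same way in one or more branches.

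For a patient already at a reduced dose, 6.6.3 speaks only of recurrence. Treatment must stop if "after treatment is resumed at a lower dose level, the toxicity recurs with the same or worse severity, except for recurrence of cytopenias". In the row for recurrent cytopenia, "no further dose reduction is allowed for already reduced dose". A footnote to Table 6-4 requires discontinuation when asymptomatic grade 3 lipase or amylase elevation returns at the reduced dose.

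On the endpoint, SAP 2.5.3 handles discontinuation before Week 48 by a composite strategy: "Treatment discontinuations due to any reason will be defined as non-responders". Dose modification and interruption follow treatment policy, so the observed BCR::ABL1 value counts.

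**The concern.** Take a patient reduced to 40 mg for one toxicity who then develops a different one that falls in a mandatory reduction branch. Once the hold ends, a lower dose breaks Table 6-3, and resuming at 40 mg departs from a mandatory reduction. Stopping is not what the row instructs. The site has to choose without a rule.

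Two things are at stake. Patients with the same toxicity history may be managed differently across sites, at any time in the 144 weeks of treatment. Before Week 48 the choice also helps decide responder status, so part of the variation in the primary endpoint would reflect how a site reads the table and not the effect of the drug.

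**Working it through.** **1. Which rows conflict.** By hand count, 19 rows of Table 6-4 end in a one-level reduction in at least one branch.

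- Fourteen are labelled Mandatory: neutropenia grades 3 and 4; febrile neutropenia; thrombocytopenia grades 3 and 4; general non-hematologic grade 3; bilirubin >3-10 x ULN; four AST/ALT rows; combined liver elevation that is treatment-related but not DILI; amylase/lipase grade 3; pancreatitis grade 2.
- Four are Recommendations: bilirubin >1.5-3 x ULN, diarrhea grade 2, rash grade 3, fatigue grade 3. The no-deviation sentence does not reach them.
- The hypertension row for systolic ≥160 or diastolic ≥100 mm Hg has no label.

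**2. Which branches conflict.** Several Mandatory rows conflict only in part:

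| Table 6-4 row | Conflicts at 40 mg | Can be followed at 40 mg |
|---|---|---|
| General non-hematologic grade 3 | restart | hold |
| Febrile neutropenia | restart | hold |
| First grade 3/4 cytopenia, patient reduced for another reason | resolved after 14 days | resolved within 14 days |
| AST/ALT >5-10 x ULN, normal baseline | resolved after 14 days | resolved within 14 days |
| AST/ALT >10-20 x ULN, normal baseline | restart | hold |
| Bilirubin >3-10 x ULN | resolved within 14 days | resolved after 14 days (discontinue) |
| Amylase/lipase grade 3 | resolved within 7 days | resolved after 7 days (discontinue) |

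**3. Whether another passage settles it.**

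- The stop rule in 6.6.3 is triggered by return of the toxicity that led to the reduction.
- The line barring further reduction sits in the recurrent-cytopenia row.
- The lipase/amylase footnote covers recurrence only.
- The 28-day (non-hematologic) and 42-day (hematologic) limits cap the hold; they do not say how to restart.
- Protocol 9.1.1 points back to Table 6-4 or to investigator judgement.

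The recurrence rules also give opposite precedents at the reduced dose: stop for a recurrent non-hematologic toxicity, no further reduction for recurrent cytopenia. A site cannot infer a default from them.

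**4. The plan's own power figure.** Inputs from Protocol 12.4.2 and 12.8.1: n = 156, null rate 0.23, alternative 0.33, exact one-sided 0.025. Let X be the number of responders.

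- P(X ≥ 46 | 0.23) = 0.0363, which is too large. P(X ≥ 47 | 0.23) = 0.0241. Rejection therefore needs 47 of 156 (30.1%).
- The Clopper-Pearson lower bound is 22.47% at 46/156 and 23.05% at 47/156, which agrees with the stated rejection rule.
- Power = P(X ≥ 47 | 0.33) = 0.801. The stated 80% is reproduced.

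**5. Illustrative size.** The documents give no count of patients at 40 mg with a new reduction-triggering toxicity. Assume 15-25% of the 156 are reduced before Week 48, and 10-20% of those have such an event:

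- low: 156 x 0.15 x 0.10 = 2.3 patients
- high: 156 x 0.25 x 0.20 = 7.8 patients

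These are patients, not responders. At a 33% response rate, if every one is stopped, the expected loss is 2.3 x 0.33 ≈ 0.8 to 7.8 x 0.33 ≈ 2.6 responders. With k lost, the expected rate is 0.33 - k/156 and power is P(X ≥ 47) at that rate:

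| Assumed patients | Share stopped | k | Expected rate | Power |
|---|---|---|---|---|
| 2.3 | all | 0.8 | 32.5% | 76% |
| 7.8 | all | 2.6 | 31.4% | 66% |
| 2.3 | half | 0.4 | 32.8% | 78% |
| 7.8 | half | 1.3 | 32.2% | 73% |

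Each lost response moves the rate by 1/156 = 0.64 percentage points.

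**The case against.** The best reply is that stopping breaks neither rule: it is not a dose below 40 mg, and it is not continued treatment at an unreduced dose. Protocol 6.1.4 allows discontinuation at the investigator's discretion, and 9.1.1 requires it where continuing would harm the participant. This stands as far as it goes. A reader might infer that every site must breach a binding rule, or that nothing in Table 6-4 can be followed at 40 mg. The documents support neither: a site can stop, and the hold, monitoring and time limits all work at 40 mg. What remains is that stopping is permitted but not instructed, and that an investigator who judges continued treatment appropriate has no compliant restart.

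On cytopenia, the recurrence row refers to any cytopenia, so it can reasonably be read to cover a second lineage after a cytopenia-driven reduction. The clear gap is therefore a first cytopenia in a patient reduced for a different reason.

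On the endpoint, discontinuation for intolerance is non-response under both Protocol 12.4.3 and SAP 2.5.3, so the variable is defined on either path, and discretion over stopping exists throughout the trial. That is correct. The gap adds to that discretion by an unknown amount and does not leave the endpoint undefined.

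On size, the 15-25% and 10-20% inputs have no source in the documents. That also stands.

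**Conclusion.** The conflict is real but limited to the restart step. It applies to a patient already at 40 mg, with a toxicity that is not a recurrence, in a Table 6-4 branch that ends in a mandatory one-level reduction. This is more than missing detail, because two stated rules cannot both be met on restart and the nearby precedents point in opposite directions.

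The finding rests on the text and not on the arithmetic. On the assumed 2 to 8 patients, a 33% response rate and every such patient stopped, at most about 0.8 to 2.6 would-be responders are lost and power is about 76% to 66%. If sites stop only some of them, the effect is smaller. A reader might be tempted to size it at four lost responders, which gives 56% power. That would need 4/0.33 ≈ 12 stopped patients, above the assumed maximum of 8, so the figure should not be used. The inconsistency in safety management stands whatever the effect on power.

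**What to change.** Reconcile Tables 6-3 and 6-4 and the text of 6.6.3. Add one statement of what applies when Table 6-4 calls for a one-level reduction in a patient already at 40 mg total daily dose and the toxicity is not a recurrence. Cross-refer to it in the cytopenia rows so that they read consistently. Which action is specified is for the sponsor's clinical team to decide.

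The cost is one sentence in the next protocol amendment, with the ethics committee and, where required, health authority approvals set out in Protocol 14.1. Amendment 01 already made a comparable clarification for recurrent grade 3/4 cytopenia. SAP 2.5.3 needs no change, because its rules apply to either course.
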